4.6. Randomisation: sequence generation

Stratified random sampling method shall be used as it allows equal distribution among each 3 ethnics as well as equal distribution for 4 supplementation groups. Each participant is masked with study code, and only the primary researcher has the master key list. Computer generated randomization of sampling into groups of four shall be used. The sample size will be divided into four groups: Placebo, 600IU/day, 1200IU/day and 4000IU/day. The divided group will then further divided equally into three ethnics group (Malays, Chinese, and Indian). The sampling method is illustrated as below:

[figure not shown]

Diagram 2: Illustration of stratified sampling method

4.7. Randomisation: allocation concealment mechanism

The supplementation of vitamin D and calcium for all 4 groups are in vegetable-capsule form and identical in appearance. The supplements will be pre-packed in plastic bottles and consecutively numbered for each participant according to the randomisation schedule. Each participant is masked with a specific study code and receives the supplementation in the corresponding pre-packed bottle.

4.8. Randomisation: implementation

The researcher assigned each participant with study code. Computer generated random number list prepared by researcher. Each enrolled participants will be sequence into the random trial list. With the specific study code, the researcher will write the subjects' study code on the blood tube before passing the tubes to the phlebotomist. After blood samples collected in the blood tubes, it will be sealed into a plastic bag and send to the lab for centrifugation. The lab process will be conducted with each specific study code as identification.

4.9. Blinding

Blinding will be strictly maintained by emphasising to intervention participants that each supplement capsules adheres to healthy and safety principles. Except for interventionist (primary researcher), investigators and participants are kept blind to supplementation assignment.

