4.1. Trial Design

This study is a stratified control trial study. It is a double-blind design, with participants randomly assigned to receive vitamin D doses of 0 IU/day, 600 IU/day, 1200 IU/day, or 4000 IU/day. The study protocol and ethics will first require approval from the International Medical University Joint Research and Ethics Committee (IMU-JC). Consent letter will be given to participants to obtain permission to participate in the study. Reasons and purpose of the study, study protocol and privacy and confidentiality will be informed. All participation shall remain as voluntary.

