The sunlight exposure of participants will be determined using a self-administered Sun Exposure Measurement Questionnaire (SEM-Q). It is a validated questionnaire widely used in other countries. Data collected from sunlight exposure measurement questionnaire (SEM-Q) in this study will be correlated with serum vitamin D.

d) Vitamin D supplementation and blood sample

Participants will be randomly divided into groups of 4 for a 16 weeks vitamin D supplementation. One of the group acts as a controlled and the other 3 grouping will be given different amount of vitamin D supplementation of 600IU/day, 1200IU/day and 4000

IU/day respectively. All groups' supplementation included 500mg/day of calcium. Blood collection will be conducted before supplementation as a baseline data, and after 16 weeks of supplementation. The baseline blood draw before supplementation served as the second-line screening of participants. The baseline blood draw served to provides researcher the basal serum 25(OH)D of participants and to exclude any hypo- or hyperthyroidism if detected. Blood drawing will be conducted by trained physicians or phlebotomists after an overnight fast. Blood sample of 5ml will be collected. The serum will be spin down, extracted and stored at -80°C until being analyzed. The serum 25(OH)D, and serum PTH will be analyzed. Serum vitamin D and PTH will be assayed using Centaur Analyser.

The supplements are provided by Fiatec Bioactive Sdn Bhd, Malaysia; where the raw ingredients are imported from DSM Nutritional Products. The products are prepared and packed into vegetable capsules, and will be analyze each to contain at least 90% of the required dosage amount. Vitamin D classification is categorized based on the recommendation of IOM. Serum 25(OH)D level lower than 30nmol/L considered as vitamin D deficiency; and level between 30-50nmol/L considered as vitamin D insufficiency (40). This part of the study is to determine the amount of vitamin required to provide optimum level of PTH, which in turns serves to indicate optimum absorption of calcium.

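### Allocation is not shown to be concealed from the research team: the primary researcher is unblinded and holds the master key, and no independent party is named for the randomisation list

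*Combined protocol and SAP*

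**What the plan says.** All references are to the combined protocol and SAP.

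- Section 4.1 gives the design label: "It is a double-blind design". No exception is stated there.
- Section 4.9 gives the exception: "Except for interventionist (primary researcher), investigators and participants are kept blind to supplementation assignment".
- Section 4.6 says of the link between participants and codes that "only the primary researcher has the master key list". It also plans a computer-generated allocation balanced over three ethnic groups and four arms.
- Section 4.7 describes capsules that look alike, in bottles packed in advance and numbered to the randomisation schedule. Each participant, under a study code, "receives the supplementation in the corresponding pre-packed bottle". Who packs and numbers the bottles is not stated.
- Section 4.8 describes implementation: "The researcher assigned each participant with study code. Computer generated random number list prepared by researcher". It continues: "Each enrolled participants will be sequence into the random trial list". The researcher also writes the "study code on the blood tube before passing the tubes to the phlebotomist", and the laboratory works from the code alone.
- Section 4.4(d) adds a second function to the first blood sample: "The baseline blood draw before supplementation served as the second-line screening of participants".

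**The concern.** Concealment and blinding depend on who can see the list. Here the one role that is openly unblinded also holds the master key, and list preparation and code assignment rest with a researcher who may be the same person. The title of interventionist suggests someone who deals with participants, although the plan does not set out the duties.

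A person who knows the arms could, without intending to, influence four things: who enters and in what order, who is excluded after the baseline sample, how diet records are clarified, and how the groups are compared. Good assays do not protect against selection at entry, unequal exclusions or choices made in the analysis. Section 4.11 leaves several such choices open. It names no ANCOVA covariates and no analysis population, so knowledge of the arms at that stage would matter more than under a tightly specified analysis.

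**Working it through.** No arithmetic applies, because no figure in the documents sizes this risk. The check is to set the steps side by side and ask who performs each one and whether that person is blind.

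| Step | Section | Who, according to the plan | Blind to arm? |
|---|---|---|---|
| Prepare random list | 4.8 | A researcher | Not stated |
| Assign study codes | 4.8 | A researcher | Not stated |
| Hold master key | 4.6 | Primary researcher only | No (4.9) |
| Pack and number bottles | 4.7 | Not named | Not stated |
| Exclude after baseline sample | 4.4(d) | Not named | Not stated |
| Clarify diet records | 4.4(b) | A researcher | Not stated |
| Assay 25(OH)D and PTH | 4.4(d), 4.8 | Laboratory, by study code | Samples coded |
| Compare groups by ANCOVA | 4.11 | Not named | Not stated |

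**1. Do the bottles close the gap?** Identical capsules and numbered bottles conceal the arm from participants and from staff who see only a number. They do not conceal it from whoever holds the list. The only active measure described in 4.9, reassuring participants about the capsules, is also aimed at participants. The bottle system does show that the exemption is unnecessary: a person handing out numbered bottles need not know the arms. The documents give no reason for the exemption.

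**2. Does it matter what the master key links?** It may link codes to names, codes to arms, or both. The answer affects how far custody of the key is a problem. It does not remove the problem, because 4.9 says separately that the primary researcher is not blind to assignment.

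**3. Is the researcher in 4.8 the primary researcher?** If so, one unblinded person prepares the list, assigns the codes and holds the key. If not, a second person prepared the list and may know the arms, unless the list carried only masked labels. The plan does not say which applies. Neither reading puts the list in the hands of someone shown to be independent.

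**4. Is allocation fixed before eligibility is known?** The code goes on the tube before the sample is drawn (4.8), the code corresponds to a bottle (4.7), and the baseline sample is also a screening step (4.4(d)). If the labelling covers the baseline sample, the code exists before the screening result. Whether the bottle is fixed by then is not stated, and "Each enrolled participants will be sequence into the random trial list" suggests that enrolment comes first. This supports asking for the order to be stated; it does not establish a fault.

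**5. Which routes could reach the results?** The exclusion tied to the baseline sample is for thyroid dysfunction, a laboratory criterion, and the eligibility criteria in 4.2 set no 25(OH)D threshold. Discretion there is limited, though no numeric thyroid cut-off is given. Diet records feed the covariate question in Objective 2; 4.11 does not name diet as an ANCOVA covariate, so a path from diet clarification to the comparison of arms is not shown. The analysis route is open because no analyst is named, blind or otherwise.

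**The case against.** The strongest reply is that the plan discloses the arrangement. Section 4.1 is a short design summary, and 4.9, the section on blinding, says who is blind and who is not. A reader might infer from the two that the double-blind label is false. The documents do not support that: participants and all other investigators are kept blind, and the exception is stated. The label in 4.1 is incomplete, and 4.9 itself qualifies it.

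A reader might also infer that participants are allocated before screening, so that the list holder can select among them. That rests on facts the plan does not give, and the reference to enrolled participants in 4.8 points the other way.

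Further, the outcomes are analyser results on coded samples, and blood is drawn only at baseline and at 16 weeks, so no interim result could guide anyone. The plan never promises a blinded analyst, so asking for one corrects no inconsistency. These points stand, and they keep the likely effect small.

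What they do not answer is the core of the point. Disclosing an exemption neither justifies it nor conceals the list, and from 4.6 to 4.9 a reader cannot establish that those enrolling participants were unaware of the next allocation.

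**Conclusion.** The point holds as a weakness in the planned safeguards that should be corrected. As written, the plan leaves one role unblinded, gives that role the master key, and names nobody independent to prepare or hold the list. Concealment from the people who may enrol, exclude, clarify diet records or analyse is therefore not shown.

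The size of any bias cannot be estimated from the documents. It is likely modest for 25(OH)D and PTH. It would be wrong to conclude that the trial's results are biased, since the plan does not say that the unblinded person performs any of the exposed steps. Confidence is medium, because the reading depends on two unstated facts: what the master key links, and whether the researcher in 4.8 is the primary researcher. Either answer still calls for a change in the text.

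**What to change.** 1. Have an existing person outside recruitment, follow-up and analysis, for example a colleague or the capsule supplier, generate and hold the ethnicity-stratified list and number the bottles from it. Keep the list sealed until database lock, with a code-break route.
2. Remove the exemption in 4.9, so that the primary researcher sees bottle numbers only. State in 4.6 what the master key links.
3. State in 4.8 who assigns the codes, and that eligibility, including the baseline screening result, is settled before a bottle number is assigned.
4. Run the ANCOVA in 4.11 on coded arms.

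If the exemption must stay, qualify the label in 4.1 to match 4.9, and have diet-record clarification and the ANCOVA done by blinded team members.

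The cost is revised wording in 4.1 (if the exemption stays), 4.6, 4.8, 4.9 and 4.11, the transfer of list preparation, custody and bottle numbering to another person, and a code-break route. This is a small administrative burden. It assumes that a suitable colleague or the supplier can take the task, which the documents do not confirm; the fallback covers the case where neither can.

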4.10. Similarity of interventions

This study is similar with a previous study by MF Holick, where healthy adults aged 18-84 year old were enrolled in his study. Subjects with chronic liver and kidney disease and those taking medications, including anticonvulsants, glucocorticoids, and barbiturates, that might affect vitamin D metabolism were excluded from the study. Recruited subjects were randomly assigned in a double-blinded fashion to receive either placebo or experimental supplementation. All subjects had blood samples collected at baseline and every week for a total of 11 week. Each subject was given a dietary questionnaire at baseline to assess vitamin D and calcium consumption (42).

4.11. Statistical methods

The dietary intakes collected from the repeated 24-hour diet recall will be entered. Using the database in Nutrient Composition of Malaysian Foods (1997) and Singapore Nutrient Composition of Foods (2003), all participants' nutrients intake will be analysed. The collected data will be converted into energy and nutrients intake using Nutritionist Pro Diet Analysis Software (NutriPro Software). Further analysis of data obtained will be carried out using Statistical Package for the Social Sciences (SPSS) version 22.0. The mean, standard deviation, and/or median, inter-quartile range will be calculated to describe the demographic background of the participants and nutrients intakes from the 24-hr diet record. Data obtained will be checked for distribution pattern, whether it is normally distributed or skewed. Analysis of covariance (ANCOVA) will be used to compare between the trial groups. To determine the relationship between several independent variables and a dependant variable, multiple regressions will be used. Bland-Altman will be used to analyze the agreement of variables. The significance level is set at $p < 0.05$.

References:

- [1] TJ Green, CM Skeaff, JEP Rockell, *et al.* Vitamin D status and its association with parathyroid hormone concentrations in women of child-bearing age living in Jakarta and Kuala Lumpur. *Eur J Clin Nutr* 2008; 62: 373-378.
- [2] Michael F. Holick. Vitamin D: A Millennium Perspective. *J Cell Biochem* 2003; 88: 296-307.
- [3] Joseph E Zerwekh. Blood biomarkers of vitamin D status. *Am J Clin Nutr* 2008; 87(suppl): 1087S-91S.
- [4] Michael F. Holick. High Prevalence of Vitamin D Inadequacy and Implications for Health. *Mayo Clin Proc.* 2006; 81(3): 353-373.
- [6] Geok L Khor, Winnie SS Chee, Zalilah M Shariff, Bee K Poh, Mohan Arumugam, Jamalludin A Rahman, Hannah E Theobald. High prevalence of vitamin D insufficiency and its association with BMI-for-age among primary school children in Kuala Lumpur, Malaysia. *BMC Public Health* 2011; 11: 95.
- [7] Chin KY, S Ima-Nirwana, Suraya Ibrahim *et al.* Vitamin D Status in Malaysian Men and Its Associated Factors. *Nutrients* 2014; 6: 5419-5433.
- [8] Nidhi Malhotra and Ambrish Mithal. Vitamin D status in Asia. International Osteoporosis Foundation (IOF).

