It has been suggested that amounts up to 4,000IU/day of vitamin D may be needed to maintain a healthy 25(OH)D level, an intake of 400IU/day may represent a minimum. There is no reported vitamin D toxicity from long-term exposure to sunlight and no published studies showing adverse effects from dietary intake of 10,000IU dosage. This dose had been set as the No Observed Adverse Effects Level (NOAEL). Doses of 4,000IU/day for 3 months and 50,000IU/week for 2 months have been administered without toxicity (39). The European food safety authority and the US health authority have set 4000 IU/day of vitamin D as the tolerable upper intake level for adolescents and adults.

CHAPTER 3: RESEARCH OBJECTIVES AND HYPOTHESIS

Objectives

1. To determine the efficacy of vitamin D supplementation on plasma 25-hydroxyvitamin D [25(OH)D] and intact parathyroid hormone (PTH) concentrations after daily intake of supplements containing 500 mg calcium with either 0 IU, 600 IU, 1200 IU or 4000 IU vitamin D for 16 weeks.
2. To assess the influence of key covariates, namely sun exposure, vitamin D dietary intake and body mass index status on plasma 25-hydroxyvitamin D [25(OH)D] and intact parathyroid hormone (PTH) of the study participants at baseline and at 16 weeks of supplementation.

Hypothesis

1. H_0 : No significant differences in mean plasma 25-hydroxyvitamin D [25(OH)D] concentrations of participants consuming daily 500 mg calcium and vitamin D supplements at 0 IU, 600 IU, 1200 IU or 4000 IU for 16 weeks
2. H_0 : No significant differences in mean plasma intact parathyroid hormone (PTH) concentrations of participants consuming daily 500 mg calcium and vitamin D supplements at 0 IU, 600 IU, 1200 IU or 4000 IU for 16 weeks
3. H_0 : No significant influence of sun exposure duration, dietary intake of vitamin D and body mass index on plasma 25-hydroxyvitamin D [25(OH)D] and intact parathyroid hormone (PTH) of the study participants at baseline and at 16 weeks of supplementation

CHAPTER 4: METHODOLOGY

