4.3. Study setting

The target study population is group of academic and support staffs and universities students in Klang Valley. A total of 120 women subjects from each major race (Malay, Chinese, Indian) in Malaysia will be recruited.

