4.5. Sample size

Calculation of sample size is done with the statistical power analysis program, G*Power 3. It covers wide statistical tests and provides improved effect size calculators (43). By obtaining the last 100 data on PTH values from local research data lab, the median for 12.5, 37.5, 62.5, 87.5th percentiles and overall standard deviation (SD) were obtained. The effect size is obtained by putting in the median and SD values into the G*Power program. Using G-power with 0.7597 (effect size), a power of 0.99 and alpha significance of 0.05, the total sample size is 48 subjects.

Hence, in consideration of the research requires follow-up of 16 weeks, with a 30% possibility of dropout rate and a various conditions of exclusion criteria, a sample size of 120 participants would be needed for invitation to the study.

[figure not shown]

Diagram 1: Screenshot of Sample Size Calculation using G-Power

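### Do the unlisted ANCOVA and regression terms (baseline marker, ethnicity, dose at week 16) mean that the analysis plan must change?

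*Combined protocol and SAP*

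**What the plan says.** Section 4.11 gives the between-arm method as "Analysis of covariance (ANCOVA) will be used to compare between the trial groups". For the covariate questions it says "To determine the relationship between several independent variables and a dependant variable, multiple regressions will be used". It gives no outcome form, covariate list or factors beyond the trial groups themselves.

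Chapter 3 is the only place where covariates are named. Objective 2 concerns "key covariates, namely sun exposure, vitamin D dietary intake and body mass index status", and the third null hypothesis begins "No significant influence of sun exposure duration, dietary intake of vitamin D and body mass index on plasma 25-hydroxyvitamin D"; both apply at baseline and at 16 weeks. No passage assigns these three variables to the ANCOVA.

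The other candidate terms will all be available. Section 4.4(d) states "Blood collection will be conducted before supplementation as a baseline data, and after 16 weeks of supplementation". Section 4.6 divides each arm equally among three ethnic groups. Assigned dose is known for every woman at analysis.

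**The concern.** Read literally, the plan's only declared covariates are sun exposure, diet and BMI. An analyst who took that as the full list could leave out three useful terms:

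- the baseline value of the marker, usually the strongest predictor of its week-16 value;
- ethnicity, which was used to balance allocation;
- dose in the week-16 regression for hypothesis 3, where the spread between arms would then sit in the residual.

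Precision would be at stake. Arm differences would have wider intervals than the data allow, and a finding of no influence for sun exposure, diet or BMI would be somewhat more likely. Validity is not at stake. Arms are randomised, so the arm comparison is sound without adjustment. For the same reason dose is independent of characteristics fixed before allocation, so leaving it out would widen their coefficients without biasing them.

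**Working it through.** **Inputs from the plan (4.3, 4.5, 4.6).** Four equal arms; effect size 0.7597, read as Cohen's f; alpha 0.05; power 0.99; total 48; 120 invited; 30% dropout. Completers: 120 × 0.70 = 84. Section 4.3 says "A total of 120 women subjects from each major race (Malay, Chinese, Indian) in Malaysia will be recruited", which can be read as 3 × 120 = 360, giving 360 × 0.70 = 252. Both are carried below.

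**Assumptions (the plan gives none of these).** The three named covariates explain R² = 0.1 to 0.3 of within-arm variance. Baseline correlates ρ = 0.5 to 0.7 with week 16. Explained variance overlaps fully, and ethnicity adds none. A smaller dose effect is taken as equally spaced means from 0 to 0.8 SD: f = (0.8/3) × √(5/4) = 0.298.

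**1. The plan's own figure.** One-way F test, λ = N f², df = (3, N − 4). At N = 44 power is 0.988; at N = 48 it is 0.994. The stated 48 reproduces for four equal groups. It rests on no covariates. Adding baseline and ethnicity (3 df) that explain nothing moves 0.9938 to 0.9935.

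**2. ANCOVA.** λ = N f² / (1 − R²), df2 = N − 4 − covariate df. The comparison is the three named covariates (3 df) against those plus baseline and ethnicity (6 df, R² replaced by the larger of R² and ρ²).

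| N | f | Named three | Plus baseline and ethnicity | Gain |
|---|---|---|---|---|
| 48 | 0.7597 | 0.997–0.9997 | above 0.999 | at most 0.003 |
| 84 | 0.298 | 0.647–0.767 | 0.734–0.893 | 0 to 0.25 |
| 252 | 0.298 | 0.992–0.999 | 0.998 or more | 0 to 0.008 |
| 252 | 0.17 | 0.652–0.772 | 0.740–0.897 | 0 to 0.25 |

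The standard-error ratio is √[(1 − max(R², ρ²)) / (1 − R²)]. For (R², ρ) = (0.3, 0.5), (0.1, 0.5), (0.3, 0.7) and (0.1, 0.7) it is 1.00, 0.91, 0.85 and 0.75.

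The size of the gain therefore depends on an assumed effect and assumed correlations, at either sample size. Replacing the three named covariates with baseline and ethnicity can lose power: with R² = 0.3, ρ = 0.5 and 84 completers, power falls by 0.03, from 0.77 to 0.74.

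**3. Week-16 regression without dose.** Residual variance is multiplied by 1 + f²: 1.089 at f = 0.298, and 1 + 0.577 = 1.577 at 0.7597. For a 1-df test with assumed partial r = 0.3, λ = N × [0.09/0.91] / (1 + f²).

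- N = 84: λ = 8.31 with dose, power 0.81. Without dose, λ = 7.63 or 5.27, power 0.78 or 0.62.
- N = 252: 0.999 with dose; 0.997 or 0.977 without.

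**4. Ethnicity in that same regression.** Sections 2.2 and 2.4 tie vitamin D status to clothing, cultural practice and skin pigmentation, so ethnicity may overlap with sun exposure. Suppose it explains 20% to 30% of sun exposure and no further outcome variance. Then λ = 8.31 × 0.8 = 6.65 or 8.31 × 0.7 = 5.82, and power at 84 falls from 0.81 to 0.72 or 0.66. If ethnicity also removes 10% of residual variance, power is 0.77 or 0.71. Each of these losses exceeds the 0.03 lost by omitting dose at f = 0.298.

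**The case for a change.** The best case for a change has three parts.

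First, f = 0.7597 is weak reassurance. Section 4.5 derives it thus: "By obtaining the last 100 data on PTH values from local research data lab, the median for 12.5, 37.5, 62.5, 87.5th percentiles". That describes the spread of existing PTH values and is not a dose effect. A smaller true effect is quite possible, and adjustment helps most there. This stands, and is why the table includes smaller effects. It shows that baseline adjustment is worth having; it does not show that the plan rules it out.

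Second, omitting dose could matter at week 16, since power falls to 0.62 at 84 completers if f really were 0.7597. The arithmetic stands. But the ANCOVA has little to gain at that effect size, so for PTH the two losses are not large together. The regression sentence speaks of several independent variables without restricting them, and an analyst of a dose trial would ordinarily include dose.

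Third, the primary researcher is unblinded (4.9) and holds the key list (4.6), so unlisted terms leave room to choose covariates after seeing results. This is a fair argument for recording the terms before the data are opened. It concerns documentation, however, and does not show that the stated methods are wrong or that precision will be lost.

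**Conclusion.** No change is called for. The text is silent, and an analyst would fill the gap sensibly: the ANCOVA already has trial group as its factor, a baseline draw exists to serve as its covariate, and dose belongs naturally in a week-16 regression.

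The arm comparisons are valid either way. At the plan's effect size the power at issue is at most 0.003. The larger figures (up to 0.25 for the ANCOVA; 0.03 to 0.19 for hypothesis 3 at 84 completers, from 0.81 − 0.78 and 0.81 − 0.62) require assumed values of R², ρ, partial r or f. They also require a model that omits baseline or dose, which the plan does not prescribe. No figure can be given for 25(OH)D, because the plan states no effect size for it.

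Whether ethnicity enters the hypothesis 3 regression is a scientific choice. Including it asks about associations within ethnic groups and may cost power.
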